8.3.4. Adverse Events

Adverse events will be reported in accordance with the sponsor reporting standards by treatment.

8.3.5. Laboratory Data

Laboratory data will be listed and summarized in accordance with the sponsor reporting standards.

The baseline measurement is the last predose measurement on Day 1 of Period 1.

8.3.6. Vital Signs Data

Vital Signs data will be databased and available upon request.

The baseline measurement is the last predose measurement on Day 1 of Period 1.

8.3.7. ECG Data

ECG data will be databased and available upon request.

The baseline measurement is the last predose measurement on Day 1 of Period 1.

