8.2.3. Electrocardiograms

Standard 12-lead ECGs utilizing limb leads (with a 10 second rhythm strip) should be collected at times specified in the **SoA** section of this protocol using an ECG machine that automatically calculates the heart rate and measures PR, QT, and QTc intervals and QRS complex. Alternative lead placement methodology using torso leads (eg, Mason-Likar) should not be used given the potential risk of discrepancies with ECGs acquired using standard limb lead placement. All scheduled ECGs should be performed after the participant has rested quietly for at least 5 minutes in a supine position.

To ensure safety of the participants, a qualified individual at the investigator site will make comparisons to baseline (Period 1, Day 1 predose) measurements. Additional ECG monitoring will occur if a) a postdose QTc interval is increased by ≥ 60 msec from the baseline **and** is > 450 msec; or b) an absolute QTc value is ≥ 500 msec for any scheduled ECG. If either of these conditions occurs, then 2 additional ECGs will be collected approximately 2 to 4 minutes apart to confirm the original measurement. If the QTc values from these repeated ECGs remain above the threshold value, then a single ECG must be repeated at least hourly until QTc values from 2 successive ECGs fall below the threshold value that triggered the repeat measurement.

If a) a postdose QTc interval remains ≥ 60 msec from the baseline **and** is > 450 msec; or b) an absolute QTc value is ≥ 500 msec for any scheduled ECG for greater than 4 hours (or sooner, at the discretion of the investigator); or c) QTc intervals get progressively longer, the participant should undergo continuous ECG monitoring. A cardiologist should be consulted if QTc intervals do not return to less than the criterion listed above after 8 hours of monitoring (or sooner, at the discretion of the investigator).

In some cases, it may be appropriate to repeat abnormal ECGs to rule out improper lead placement as contributing to the ECG abnormality. It is important that leads be placed in the same positions each time in order to achieve precise ECG recordings. If a machine-read QTc value is prolonged, as defined above, repeat measurements may not be necessary if a qualified medical provider's interpretation determines that the QTc values are in the acceptable range.

ECG values of potential clinical concern are listed in [Appendix 7](#).

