9. STATISTICAL CONSIDERATIONS

Detailed methodology for summary and statistical analyses of the data collected in this study is outlined here and further detailed in a SAP, which will be maintained by the sponsor. The SAP may modify what is outlined in the protocol where appropriate; however, any major modifications of the primary endpoint definitions or their analyses will also be reflected in a protocol amendment.

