9.3.2. Other Safety Analyses

All safety analyses will be performed on the safety population.

AEs, ECGs, BP, pulse rate, and safety laboratory data will be reviewed and summarized on an ongoing basis during the study to evaluate the safety of participants. Any clinical laboratory, ECG, BP, and pulse rate abnormalities of potential clinical concern will be described. Safety data will be presented in tabular and/or graphical format and summarized descriptively, where appropriate.

Medical history and physical examination information, as applicable, collected during the course of the study will be considered source data and will not be required to be reported, unless otherwise noted. However, any untoward findings identified on physical examination conducted during the active collection period will be captured as AEs, if those findings meet the definition of an AE. Data collected at screening that are used for inclusion/exclusion criteria, such as laboratory data, ECGs, and vital signs, will be considered source data, and will not be required to be reported, unless otherwise noted. Demographic data collected at screening will be reported.

CC1

CC1

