6.2. Safety Endpoints

Any events occurring following start of treatment or increasing in severity will be counted as treatment emergent.

Events that occur in a non-treatment period (for example, Washout or Follow-up) will be counted as treatment emergent and attributed to the previous treatment taken.

The following data are considered in standard safety summaries (see protocol for collection days and list of parameters):

- *adverse events,*
- *laboratory data,*
- *vital signs data,*
- *ECG results.*

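### Does the absence of a planned table or listing for vital signs and ECG in the SAP leave a safety-reporting gap that needs a change?

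*SAP*

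**What the plan says.** SAP 6.2 introduces a four-item list (adverse events, laboratory data, vital signs, ECG results) with "The following data are considered in standard safety summaries". SAP 8.3 then sets the outputs:

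- 8.3.4: "Adverse events will be reported in accordance with the sponsor reporting standards by treatment"
- 8.3.5: "Laboratory data will be listed and summarized in accordance with the sponsor reporting standards"
- 8.3.6: "Vital Signs data will be databased and available upon request"
- 8.3.7: "ECG data will be databased and available upon request"

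Sections 8.3.6 and 8.3.7 each also define a baseline. SAP 8.3.8, for other safety data, is empty.

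Protocol 9.3.2 and the synopsis say that ECG, blood pressure and pulse rate are reviewed and summarized during the study, and then: "Any clinical laboratory, ECG, BP, and pulse rate abnormalities of potential clinical concern will be described". The next sentence there, on tables and graphs, applies only where appropriate. Protocol section 9 states: "The SAP may modify what is outlined in the protocol where appropriate". It asks for a protocol amendment only when the primary endpoint definitions or their analyses undergo a major change.

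The secondary safety endpoint in Protocol 3 consists of safety laboratory tests and adverse event monitoring. ECG and vital signs are not named there, although Protocol 4.1 includes them in the general monitoring of safety.

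**The concern.** Read side by side, SAP 6.2 and SAP 8.3.6–8.3.7 appear to disagree. One section places vital signs and ECG among the data for standard summaries, and the other two keep them in the database. The reference to sponsor reporting standards in 8.3.4 and 8.3.5 is missing from 8.3.6 and 8.3.7, so a listing cannot be inferred from it. Each of the two sections defines a baseline that no planned output uses, which suggests that they were not reconciled with 6.2. One programmer might produce tables and another none.

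The second strand is the protocol's promise to describe abnormalities of potential clinical concern. That sentence carries no qualifier of its own, and the SAP assigns it to no output. Protocol 8.2.3 says "ECG values of potential clinical concern are listed in" Appendix 7, and the first group of findings there only may qualify as adverse events. A QTcF value could therefore meet an Appendix 7 criterion, not be called an adverse event, and appear in no planned output. At stake is completeness of safety reporting, not the pharmacokinetic estimates.

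**Working it through.** The plan states no figure on this point. The check compares the texts and then sizes the data affected.

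**1. Outputs by data type**

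| Data type in SAP 6.2 | Output section | Planned output |
|---|---|---|
| Adverse events | SAP 8.3.4 | Reported by treatment |
| Laboratory data | SAP 8.3.5 | Listed and summarized |
| Vital signs | SAP 8.3.6 | None; held in the database |
| ECG | SAP 8.3.7 | None; held in the database |

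So 4 − 2 = 2 data types have no planned output. This part of the concern is correct.

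**2. Do the two SAP texts contradict each other?** SAP 6.2 sits under endpoints and says which data are considered. It does not say that each type will have its own table. Section 8.3 is where outputs are specified, and a specific instruction ordinarily governs a general list. Keeping data available on request is a reporting tier that the SAP uses on purpose: SAP 8.3.10 treats screening data the same way. A baseline definition still has a use when someone requests the data.

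**3. Is the protocol's sentence unmet?** It applies only if an abnormality of potential clinical concern occurs, and it prescribes no table or listing. A narrative sentence in the study report would satisfy it. SAP silence on the format is not a plan to omit it.

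**4. What other routes capture such findings?**
- Protocol 10.3.1: abnormal ECG or vital-sign results that the investigator considers clinically significant are adverse events, so SAP 8.3.4 reports them by treatment.
- Protocol 8.2.3: post-dose ECGs are compared with baseline as they are taken. Repeat recordings, continuous monitoring and cardiology consultation follow if QTc criteria are met.

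**5. How much data is affected?** The inputs are 18 participants (Protocol 9.5), assumed to complete, and the collection times in footnote g of the Schedule of Activities. On study these are Period 1 Day 1 predose and Period 3 Day 7, plus any early-termination visit.

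- Scheduled on-study readings: 18 × 2 = 36 ECGs and 36 sets of vital signs.
- Of these, post-dose: 18 × 1 = 18 of each.
- Post-dose readings per treatment: each treatment falls in Period 3 for two of the six sequences, with 3 participants per sequence in Protocol Table 3, so 2 × 3 = 6.

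Day 7 is 144 h after dosing. With the half-life in Protocol 4.1 (mean 34 h, range 18 to 55 h), and simple exponential decline counted from dosing, the fraction remaining is 2^(−144/t½):

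| t½ (h) | Half-lives, 144/t½ | Remaining |
|---|---|---|
| 34 | 4.24 | 5.3% |
| 55 | 2.62 | 16.3% |
| 18 | 8.00 | 0.39% |

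The schedule has no post-dose ECG or vital signs after the first two doses, so no within-participant comparison of treatments is possible. A by-treatment summary would rest on 6 participants per group, each measured late in elimination.

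**The case for a change.** The strongest case for a change is that holding data in a database is not summarizing it, and that the same list in SAP 6.2 covers adverse events and laboratory data, which do receive outputs. The permission in Protocol section 9 lets the SAP depart from the protocol, but it cannot settle a tension between two SAP sections, and the SAP does not present 8.3.6 or 8.3.7 as a departure. Adverse event reporting covers only part of the ground, because it depends on the investigator's judgment and Appendix 7 leaves room for flagged findings that are not adverse events. A listing would be cheap, since the data are already collected.

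Much of this stands as description. The passages do not match neatly, no SAP section says how the protocol's descriptive sentence will be met, and the visible text gives no criteria of concern for blood pressure or pulse rate. What does not stand is the step from there to a needed change. A summary table of all values would go beyond the protocol's sentence, which covers only abnormalities. A protocol amendment is not called for under Protocol section 9, because no primary endpoint or analysis is involved. A listing would make reporting more complete but would alter no estimate, comparison or conclusion.

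**Conclusion.** No change to the plan is needed. The point is a small mismatch of wording between a general list in SAP 6.2 and the specific output sections 8.3.6 and 8.3.7, together with a descriptive commitment whose format is left to the report's authors. Analysts and medical writers can fill that sensibly: keep the data retrievable, report clinically significant findings as adverse events, and describe any other value of concern in the text of the report.

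The size is 2 of 4 data types without a planned output, and 18 scheduled post-dose readings of each kind, all at 144 h after the third dose with about 5% of the drug remaining at the mean half-life. The primary pharmacokinetic comparisons and the named safety endpoint are untouched.

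This rests on three assumptions: that 18 participants complete, with early-termination or unscheduled readings adding to the counts; that investigators apply the adverse event definition in Protocol 10.3.1 to ECG and vital-sign findings; and that the study report honours the protocol's sentence on abnormalities if any occur. The content of the sponsor's standard summaries cannot be seen from these documents, and the conclusion does not depend on it.

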8.3.8. Other Safety Data

None.

8.3.9. Concomitant Treatments

All concomitant medication(s) as well as non-drug treatment(s) will be provided in the listings.

8.3.10. Screening and Other Special Purpose Data

Screening data will be available upon request.

10. APPENDICES

Appendix 1. SAS CODE FOR ANALYSES

An example of the PROC MIXED code is provided below:

Comparison of Treatment A (100 mg x 5 with applesauce under fed condition) and B (100 mg x 5 with full fat yogurt under fed condition) versus Treatment C (100 mg x 5 under fed condition);

```
proc mixed data=tab.pk;
  class seq period trt subject;
  model l&var=seq period trt/ ddfm=KR;
  random subject(seq) /subject=subject(seq);
  lsmeans trt;
  estimate 'Treatment A vs Treatment C ' trt  1  0  -1 /cl alpha=0.1;
  estimate 'Treatment B vs Treatment C ' trt  0  1  -1 /cl alpha=0.1;
  ods 'Estimates' out=est&var;
  ods 'lsmeans' out=ls&var;
  ods 'covparms' out=cov&var;
  ods 'tests3' out=tst&var;
run;
```

/* Letter assignments for treatments (trt) within the estimate statement above are as follows;

Treatment A (Test): Contents of 500 mg (100 mg x 5) bosutinib capsules mixed with 45 mL of applesauce under fed condition.

Treatment B (Test): Contents of 500 mg (100 mg x 5) bosutinib capsules mixed with 45 mL of full fat yogurt under fed condition

Treatment C (Reference): 500 mg (100 mg x 5) bosutinib intact capsules under fed condition.
*/
